9.2 Demographics and Subject Disposition

Subject disposition will be listed. The demographic variables age, sex, race, ethnicity, body weight, height and body mass index will be summarized and listed. All other demographic variables will be listed.

9.3 Pharmacokinetic Assessment

9.3.1 Pharmacokinetic Analysis

The PK parameter estimates will be determined using non-compartmental procedures in validated software program (Phoenix WinNonlin Version 6.4.1 or later).

Plasma concentrations of LY3074828 will be used to determine the following PK parameters, when possible:

Parameter	Units	Definition
AUC(0-t _{last})	day* μ g/mL	area under the concentration versus time curve from time zero to time t, where t is the last time point with a measurable concentration
DN-AUC(0-t _{last})	NA	dose normalized area under the concentration versus time curve from time zero to time t, where t is the last time point with a measurable concentration
AUC(0- ∞)	day* μ g/mL	area under the concentration versus time curve from zero to infinity
DN-AUC(0- ∞)	NA	dose normalized area under the concentration versus time curve from zero to infinity
%AUC(t _{last} - ∞)	%	percentage of AUC(0- ∞) extrapolated
C _{max}	μ g/mL	maximum observed drug concentration
DN-C _{max}	NA	dose normalized maximum observed drug concentration
t _{max}	day	time of maximum observed drug concentration
t _{1/2}	day	half-life associated with the terminal rate constant (λ_z) in non-compartmental analysis
CL/F	L/day	apparent total body clearance of drug calculated after extra-vascular administration
V _{Z/F}	L	apparent volume of distribution during the terminal phase after extra-vascular administration
V _{SS/F}	L	apparent volume of distribution at steady state after extra-vascular administration

Additional PK parameters may be calculated, as appropriate. The software and version used for the final analyses will be specified in the CSR. Any exceptions or special handling of data will be clearly documented within the final study report.

Formatting of tables, figures and abbreviations will follow the Eli Lilly Global PK/PD/TS Tool: NON-COMPARTMENTAL PHARMACOKINETIC STYLE GUIDE. The version of the tool effective at the time of PK analysis will be followed.

General PK Parameter Rules

- Actual sampling times will be used in the final analyses of individual PK parameters, except for non-bolus pre-dose sampling times which will be set to zero. For non-bolus, multiple dose profiles, the pre-dose time will be set to zero unless a time deviation falls outside of the protocol blood collection time window which is considered to impact PK parameter derivation.
- C_{\max} and t_{\max} will be reported from observed values. If C_{\max} occurs at more than one time point, t_{\max} will be assigned to the first occurrence of C_{\max} .
- AUC parameters will be calculated using a combination of the linear and logarithmic trapezoidal methods (linear-log trapezoidal rule). The linear trapezoidal method will be applied up to t_{\max} and then the logarithmic trapezoidal method will be used after t_{\max} . The minimum requirement for the calculation of AUC will be the inclusion of at least three consecutive plasma concentrations above the lower limit of quantitation (LLOQ), with at least one of these concentrations following C_{\max} . AUC(0- ∞) values where the percentage of the total area extrapolated is more than 20% will be flagged. Any AUC(0- ∞) value excluded from summary statistics will be noted in the footnote of the summary table.
- Half-life ($t_{1/2}$) will be calculated, when appropriate, based on the apparent terminal log-linear portion of the concentration-time curve. The start of the terminal elimination phase for each subject will be defined by visual inspection and generally will be the first point at which there is no systematic deviation from the log-linear decline in plasma concentrations. Half-life will only be calculated when a reliable estimate for this parameter can be obtained comprising of at least 3 data points. If $t_{1/2}$ is estimated over a time window of less than 2 half-lives, the values will be flagged in the data listings. Any $t_{1/2}$ value excluded from summary statistics will be documented in the footnote of the summary table.
- A uniform weighting scheme will be used in the regression analysis of the terminal log-linear portion of the concentration-time curve.
- The parameters based on the observed last quantifiable drug concentration (C_{last}) will be reported.

Individual PK Parameter Rules

- Only quantifiable concentrations will be used to calculate PK parameters with the exception of special handling of certain concentrations reported below the lower limit of quantitation (BQL). Plasma concentrations reported as BQL will be set to a value of zero when all of the following conditions are met:
 - The compound is non-endogenous.
 - The samples are from the initial dose period for a subject.

- The time points occur before the first quantifiable concentration.
- All other BQL concentrations that do not meet the above criteria will be set to missing.
- Also, where two or more consecutive concentrations are BQL towards the end of a profile, the profile will be deemed to have terminated and therefore any further quantifiable concentrations will be set to missing for the calculation of the PK parameters unless it is considered to be a true characteristic of the profile of the drug.

Individual Concentration vs. Time Profiles

- Individual concentrations will be plotted utilizing actual sampling times.
- The terminal point selections will be indicated on a semi-logarithmic plot.

Average Concentration vs. Time Profiles

- The average concentration profiles will be graphed using scheduled (nominal) sampling times.
- The average concentration profiles will be graphed using arithmetic average concentrations.
- The pre-dose average concentration for single-dose data from non-endogenous compounds will be set to zero. Otherwise, only quantifiable concentrations will be used to calculate average concentrations.
- Concentrations at a sampling time exceeding the sampling time window specified in the protocol, or $\pm 10\%$, will be excluded from the average concentration profiles.
- Concentrations excluded from the mean calculation will be documented in the final study report.
- A concentration average will be plotted for a given sampling time only if 2/3 of the individual data at the time point have quantifiable measurements that are within the sampling time window specified in the protocol or $\pm 10\%$. An average concentration estimated with less than 2/3 but more than 3 data points may be displayed on the mean concentration plot if determined to be appropriate and will be documented within the final study report.

Treatment of Outliers during Pharmacokinetic Analysis

Application of this procedure to all PK analyses is not a requirement. Rather, this procedure provides justification for exclusion of data when scientifically appropriate. This procedure describes the methodology for identifying an individual value as an outlier for potential exclusion, but does not require that the value be excluded from analysis. The following methodology will not be used to exclude complete profiles from analysis.

Data within an Individual Profile

A value within an individual profile may be excluded from analysis if any of the following criteria are met:

- For PK profiles during single dosing of non-endogenous compounds, the concentration in a pre-dose sample is quantifiable.
- For any questionable datum that does not satisfy the above criteria, the profile will be evaluated and results reported with and without the suspected datum.

Data between Individual Profiles

1. If $n < 6$, then the dataset is too small to conduct a reliable range test. Data will be analyzed with and without the atypical value, and both sets of results will be reported.
2. If $n \geq 6$, then an objective outlier test will be used to compare the atypical value to other values included in that calculation:
 - a. Transform all values in the calculation to the logarithmic domain.
 - b. Find the most extreme value from the arithmetic mean of the log transformed values and exclude that value from the dataset.
 - c. Calculate the lower and upper bounds of the range defined by the arithmetic mean $\pm 3*SD$ of the remaining log-transformed values.
 - d. If the extreme value is within the range of arithmetic mean $\pm 3*SD$, then it is not an outlier and will be retained in the dataset.
 - e. If the extreme value is outside the range of arithmetic mean $\pm 3*SD$, then it is an outlier and will be excluded from analysis.

If the remaining dataset contains another atypical datum suspected to be an outlier and $n \geq 6$ following the exclusion, then repeat step 2 above. This evaluation may be repeated as many times as necessary, excluding only one suspected outlier in each iteration, until all data remaining in the dataset fall within the range of arithmetic mean $\pm 3*SD$ of the log-transformed values.

Reporting of Excluded Values

Individual values excluded as outliers will be documented in the final report. Approval of the final report will connote approval of the exclusion.

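### SAP 9.3.1 both permits and requires exclusion of a between-profile PK outlier, leaves the comparison set and the scope of exclusion open, and asks for no with-and-without result at n ≥ 6

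*SAP*

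**What the plan says.** SAP 9.3.1, under Treatment of Outliers during Pharmacokinetic Analysis, begins with general statements. "Application of this procedure to all PK analyses is not a requirement". The procedure supplies a justification for exclusion where that is scientifically appropriate. It identifies a candidate value but "does not require that the value be excluded from analysis". It is not to be used to remove complete profiles.

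Specific rules follow:

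- **Within a profile.** A quantifiable pre-dose concentration may be excluded. For any other questionable value, "the profile will be evaluated and results reported with and without the suspected datum".
- **Between profiles, fewer than six values.** "Data will be analyzed with and without the atypical value, and both sets of results will be reported".
- **Between profiles, six or more values.** In this case "then an objective outlier test will be used to compare the atypical value to other values included in that calculation". Values are logged, the one furthest from the mean is set aside, and mean ± 3 SD is formed from the rest. A value inside that range is kept; if it lies outside, "then it is an outlier and will be excluded from analysis" (step 2e). The test may be repeated, one value at a time and with at least six values left, "until all data remaining in the dataset fall within the range".

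Excluded values are documented in the final report, and "Approval of the final report will connote approval of the exclusion".

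SAP 9.3.2 fits one linear model to the three formulations and contains no outlier rule. Protocol 10.3 defines the PK set as all data from dosed, randomized subjects with evaluable PK data, also without an outlier rule. SAP 3 says that substantial differences from the protocol will be identified; SAP 11 lists none.

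**The concern.** The plan leaves four things open for the same set of AUC or Cmax values: whether to invoke the test (what makes a value atypical is undefined), whether a flagged value must go, which values it is compared with, and which analysis it leaves. The study is open-label, so these choices can be made with the values and the arm labels in view, even though the SAP itself is to be signed off before first dosing.

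What is at stake is the reported primary ratio and its 90% CI. A 3-SD rule applied to small samples of clean data regularly removes valid extreme values. The residual variance then comes out too small and the interval too narrow. Listings and documentation show which value was removed, but they do not give the reader the model result with that value kept.

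**Working it through.** **Text.** The introduction makes two separate statements: running the procedure is optional, and an identified value need not be excluded. Step 2e contradicts the second. The comparison set is given only as the values in the calculation concerned. An arm-level summary and the three-arm model are different calculations, so within-arm and pooled testing are both open. The SAP 9.3.1 rules for AUC(0-∞) and half-life speak of values excluded from summary statistics, whereas step 2e speaks of analysis without saying which.

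**Inputs.** SAP 7: CV 49% for AUC and 23% for Cmax, 16 evaluable per arm (18 enrolled), 90% CI. The log-scale SD for AUC is sqrt(ln(1 + 0.49²)) = 0.464.

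**The plan's own figure.** The half-length not exceeded with 90% probability is t(0.95, df) × 0.464 × sqrt(2/16) × sqrt(χ²(0.90, df)/df). This gives 0.322 with df = 30 (two arms) and 0.311 with df = 45 (three-arm model). The stated 0.32 is reproduced, so SD 0.464 is the right scale.

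**How often clean data are flagged.** The expected number of values flagged in the first round is n × P(|t(n−2)| > 3/sqrt(1 + 1/(n−1))), which is also an upper bound on the chance of any exclusion:

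- n = 16: 16 × 0.0115 = 0.18
- n = 18: 18 × 0.0101 = 0.18
- pooled n = 48: 48 × 0.00474 = 0.23

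Simulating the iterated rule gives 18.3% per arm at n = 16 and 22.0% at n = 48. For the two arms in the primary contrast, 1 − (1 − 0.183)² = 0.33.

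**Size of one removal.** Dropping a value that lies 3 SD from the mean of the other 15, with SD 0.464, moves that arm's log mean by 3 × 0.464/16 = 0.087, about 9% on the ratio.

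**Effect on the primary contrast.** This used 60,000 simulated three-arm trials per setting: clean lognormal data, 16 per arm, the rule always applied and carried into the model. Pooled testing is taken on dose-normalized values. True ratios of 1.0 and 0.8 (both solution arms against Reference) are assumptions, as the documents give none.

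| | All data | Within arm | Pooled |
|---|---|---|---|
| Value removed from Reference or Test 1 | – | 33–34% | 16% |
| Median factor on the ratio in those trials | – | 1.08 | 1.09 |
| Mean CI width against all data | – | 3.6% narrower | 2.0–2.1% narrower |
| 90% CI coverage, true ratio 1.0 | 90.1% | 87.1% | 90.0% |
| 90% CI coverage, true ratio 0.8 | 90.1% | 87.1% | 89.5% |
| Mean signed shift of log ratio | – | 0.000 | 0.000 at 1.0; 0.009 toward 0 at 0.8 |

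The two readings remove different values from Reference or Test 1 in 29–30% of trials. A separate run of 15,000 trials per setting gave coverage of 86.5–86.9% within arm, 89.4% pooled, and 89.4–90.0% with all data.

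**Less than routine use.** If half the arms are trimmed, a value leaves Reference or Test 1 in 18% of trials and coverage is 88.6–88.7%. If a quarter are trimmed, the figures are 9% and 89.3%.

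**Cmax.** The log SD is sqrt(ln(1 + 0.23²)) = 0.227. The within-arm median log shift scales from 0.076 to 0.076 × 0.227/0.464 = 0.037, a factor of about 1.04.

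**The case against.** **The reporting rules follow a pattern.** Where an objective criterion exists (a quantifiable pre-dose sample, or the 3-SD test), the SAP excludes and documents. Where none exists (other within-profile values, or fewer than six values, which it calls too few for a reliable range test), it reports both ways. A reader might infer that n ≥ 6 is the one gap in an otherwise universal rule of dual reporting. The text does not support that, because a quantifiable pre-dose value may also be dropped without it. This stands. But the pattern relies on the test being objective, and a test that is optional to run, optional to act on and silent on its comparison set is objective only in its arithmetic.

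**The introduction may make only the running of the test optional.** This fails, because it says separately that an identified value need not be excluded.

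**Complete profiles are protected, and use is limited to what is scientifically appropriate.** Both limits are real. Neither clearly bars dropping one subject's AUC from the model while the concentration profile stays in place.

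**Removal from the primary model is inferred.** This stands. A reader might infer that the SAP orders valid values out of the primary model and so plans an interval with 87% coverage. It does not: use is discretionary, and SAP 9.3.2 mentions no outlier rule.

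**SAP 11 is not shown to be wrong.** A reader might infer a breach of the protocol's all-data set. That set is limited to evaluable PK data, a term left undefined, and SAP 3 promises to identify only substantial differences. Whether this is one is a judgement.

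**The effect is modest.** A median log shift of 0.076 compares with a mean CI half-length of about 0.274. The within-arm rule has no direction on average, and the protocol sets no equivalence margin, so no pass or fail changes.

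**Conclusion.** The contradiction between the introduction and step 2e is plain on the text. So are the unnamed comparison set, the undefined scope of exclusion, and the absence of any required with-and-without result at n ≥ 6, the branch that every planned arm falls into. This is more than missing detail: step 2e applied as written, within arm and through to the model, would make the primary CI too narrow.

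At that ceiling, about 33% of trials lose a valid value from Reference or Test 1, and 90% CI coverage is about 87% instead of 90%. Under the pooled reading coverage is close to nominal. The figures assume lognormal AUC with CV 49%, 16 per arm and no true outliers. They are a ceiling on use of the rule, not on the shape of the data. With heavier tails (t with 4 df, same SD, true ratio 1; an assumption) within-arm coverage is 85.6% and pooled 89.8%. The correction should be made, but the matter does not threaten the study's conclusions by itself.

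**What to change.** Reword step 2e so that the 3-SD rule flags a value and does not exclude it, in line with the introduction to the procedure. Base the headline primary and secondary inference in SAP 9.3.2 on all evaluable values in the PK population. Report the same model without flagged values as a sensitivity analysis. State whether the test is run within arm or on the pooled three-arm data, and whether any exclusion concerns the summary statistics, the model or both. If exclusion from the model is nevertheless intended, the sponsor should consider whether it is a substantial difference to be listed in SAP 11.

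The cost is SAP wording and one extra model run. For clean lognormal data, the headline CI is at most about 4% wider on average than under routine within-arm trimming (1/0.964 = 1.037), and about 2% wider than under pooled trimming. With the heavier-tailed data above, the gap against within-arm trimming would be larger (mean half-length 0.269 against 0.222), but the narrower interval is the one that covers only 85.6%.

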9.3.2 Pharmacokinetic Statistical Methodology

Log-transformed DN-AUC($0-\infty$), DN-AUC($0-t_{last}$), and DN- C_{max} will be evaluated in a linear fixed-effects model with a fixed effect for formulation. If leakage occurs frequently, whether injection-site leakage occurred (yes/no) may also be included as a covariate in the model. Furthermore, if leakage is found to be significant, the amount of leakage will also be added to the

model. The formulation differences will be back transformed to present the ratios of geometric least squares means and the corresponding 90% CI.

A single linear model with contrasts will be used for all of the following comparisons:

- Primary objective: CCI LY3074828 PFS solution formulation versus CCI LY3074828 lyophilized formulation
- Secondary Objective: CCI LY3074828 PFS solution formulation versus CCI LY3074828 PFS solution formulation
- Secondary Objective: CCI LY3074828 PFS solution formulation versus CCI LY3074828 lyophilized formulation

Example SAS code:

```
proc mixed data=xxx;
  by parameter;
  class formulation ISLoccur;
  model log_pk = formulation ISLoccur ISLamount / residual;
  lsmeans formulation / alpha=0.1 cl pdiff;
  ods output lsmeans=lsmeans;
  ods output diffs=diffs;
run;
```

The tmax will be analyzed using a Wilcoxon rank sum test for all of the above comparisons. Estimates of the median difference, 90% CIs, and p-values from the Wilcoxon rank sum test will be calculated.

Additional PK analyses may be conducted if deemed appropriate.

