## 2. Schedule of Activities

## Study Schedule Protocol I6T-MC-AMAE

Procedure	Screening	Days														Comments
		≤ 28 days	-1	1	2	4 ±1d	8 ±1d	11 ±1d	15 ±2d	22 ±2d	29 ±2d	43 ±2d	57 ±3d	71 ±3d	85/ED ±3d	
Informed consent	X															
Review / confirm inclusion/exclusion criteria	X	X														Any time prior to dosing.
Subject admission to CRU		X														
Subject discharge from CRU				X												
Outpatient visit	X				X	X	X	X	X	X	X	X	X	X	X	
LY3074828 dose			X													
Medical history	X															
Weight, height, and BMI	X															
Vital signs: blood pressure, pulse rate, temperature (hour)	X	X	Predose, 2, 6	24	72	168	240	336	504	672	1008	1344		X		Times with respect to start of dosing. Single ECGs to be collected. Time allowance for 2, 6, and 24 hour timepoints: ±15, ±30, and ±90 minutes, respectively.
12-lead ECG (hour)	X		Predose, 2, 6	24	72	168		336		672		1344		X		
Physical examination / medical assessment		X		X									X		X	Full physical examination/medical assessment at Day -1 and ED. Symptom directed physical examination/ medical assessment at all other timepoints, and as deemed necessary by the investigator.
AE review	X	X	X	X	X	X	X	X	X	X	X	X	X	X		AE only after signing ICF.
QuantiFERON®-TB Gold test	X															
Serology	X															
Ethanol test and urine drug screen	X	X														May be repeated at the discretion of the investigator.
FSH / Serum pregnancy test	X	X									X		X		X	Serum pregnancy tests for female subjects of childbearing potential only. For women who are considered to be postmenopausal, FSH should be drawn at screening to confirm postmenopausal status as defined in inclusion

Procedure	Screening	Days													Comments
		$\leq 28$ days	-1	1	2	4 $\pm 1$ d	8 $\pm 1$ d	11 $\pm 1$ d	15 $\pm 2$ d	22 $\pm 2$ d	29 $\pm 2$ d	43 $\pm 2$ d	57 $\pm 3$ d	71 $\pm 3$ d	85/ED $\pm 3$ d
															criterion [1b]; women with confirmed postmenopausal status can be exempted from further pregnancy tests during the study.
Clinical chemistry, hematology, and urinalysis	X	X			X				X		X		X		
Injection-site assessment for erythema, induration, categorical pain, pruritus, and edema (hour)		0, 0.25	24		168		336								Times with respect to start of dosing. 0 hour assessments within 5 minutes following injection. Time allowance for 0.25-hour assessment is $\pm 5$ minutes. Additional assessments performed if deemed necessary by the investigator.

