### 5.4. Scientific Rationale for Study Design

Conducting the study in healthy subjects mitigates the potential confounding effects of the disease state and concomitant medications in patients. Healthy subjects are frequently used in the assessment of bioavailability of both small and large molecules.

Single doses of LY3074828 and the PK sampling timepoints have been selected to generate PK profiles sufficient to fulfill the study objectives. As the primary endpoints of this study are

PK-related and are not subject to bias, it is not considered necessary for this study to be blinded. Subjects and site staff will be aware of the administration route.

A parallel-group design was chosen because a crossover design is impractical for compounds that have long half-lives, such as monoclonal antibodies. Additionally, a crossover study design could confound PK data if subjects develop neutralizing ADAs.

Monoclonal antibody therapy has been associated with hypersensitivity reactions, including injection-site reactions. Follow-up details on injection-site reactions will be collected by the investigative site regarding the severity, duration, type, and timing of the start of the event in relation to the start of study drug administration in order to further characterize these events.

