## 7.2. Method of Treatment Assignment

Subjects will be randomized to 1 of 3 treatment arms (CC1 LY3074828 lyophilized formulation [Reference], CC1 LY3074828 solution formulation [Test 1], or 500 mg LY3074828 solution formulation [Test 2]). Those that are randomized to receive the lyophilized formulation will be further randomized to 1 of 4 treatment sequences:

Sequence	First Injection	Second Injection
1	CC1 administered into left lower quadrant	CC1 administered into right lower quadrant
2	CC1 administered into right lower quadrant	CC1 administered into left lower quadrant
3	CC1 administered into left lower quadrant	CC1 administered into right lower quadrant
4	CC1 administered into right lower quadrant	CC1 administered into left lower quadrant

For all sequences, the third injection will comprise a 1.0 mL injection administered into an upper quadrant.

Randomization will be performed using a computer-generated randomization schedule.

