## 10. Statistical Considerations and Data Analysis

### 10.1. Sample Size Determination

Approximately 54 subjects (18 per treatment arm) may be enrolled to allow evaluable data from 16 subjects from each treatment arm to be obtained. The estimated total variability (coefficient of variation) in  $AUC(0-\infty)$ ,  $AUC(0-t_{last})$ , and maximum observed drug concentration ( $C_{max}$ ) was 49%, 49%, and 23%, respectively, in Study AMAA following a single SC dose of 120 mg LY3074828. The coefficient of variation of 49% was used for precision estimates and is assumed for all treatment arms. A sample size of 48 subjects will provide a precision, in log scale, of approximately 0.32 for the geometric means ratio in  $AUC(0-\infty)$ ,  $AUC(0-t_{last})$ , and  $C_{max}$  of lyophilized to solution formulation in log scale. That is, there is a 90% probability that the half-length of the 90% confidence interval (CI) of the geometric means ratio in log scale is not larger than 0.32. Subjects who are randomized but not administered treatment, or subjects (maximum of 6) that are administered treatment but do not have PK and ADA samples collected up to and including Day 57, may be replaced to ensure that approximately 16 subjects from each treatment arm may complete the study.

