#### 10.2.2. Study Participant Characteristics

The subject's age, sex, weight, BMI, height, race/subrace, and other demographic data will be summarized by treatment and overall.

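### The PK model prespecifies no baseline covariate; adding log screening body weight, which is already collected, is a cheap option that may narrow the primary confidence interval

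*SAP*

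**What the plan says.** SAP 9.3.2 states that log DN-AUC(0-∞), DN-AUC(0-tlast) and DN-Cmax "will be evaluated in a linear fixed-effects model with a fixed effect for formulation", and Protocol 10.3.2.2 describes the same model. The SAP fits one linear model to all three arms and takes the primary and both secondary comparisons from it as contrasts.

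The only covariates named concern leakage. If leakage is frequent, "whether injection-site leakage occurred (yes/no) may also be included as a covariate in the model", and the amount may follow. Both are recorded after the injection, so neither is a baseline covariate. The example SAS code has no weight term.

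The Protocol's Schedule of Activities lists "Weight, height, and BMI" at screening. The planned use is descriptive: in Protocol 10.2.2, "weight, BMI, height, race/subrace, and other demographic data will be summarized by treatment and overall"; in SAP 9.2, "body weight, height and body mass index will be summarized and listed". On allocation, Protocol 7.2 says "Randomization will be performed using a computer-generated randomization schedule" and names no stratification factor.

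Protocol 10.1 and SAP section 7 base the sample size on precision. With 48 evaluable subjects and a CV of 49%, the half-length of the 90% interval for the log ratio should be at most about 0.32 with 90% probability.

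**The concern.** Protocol 5.4 explains that "A parallel-group design was chosen because a crossover design is impractical for compounds that have long half-lives". The formulation comparison is therefore between subjects, and all between-subject variability enters its standard error. Doses are fixed by arm and do not depend on body size, and eligibility allows a BMI from 18.0 to 32.0 kg/m². Dose normalization removes differences in dose between arms but leaves differences in weight between subjects. If exposure depends on weight, that share of the variance stays in the residual of the primary ratio.

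Precision is at stake, not validity. The unadjusted interval already allows for chance imbalance in weight, so adjustment would not correct a bias. Both documents permit additional PK analyses, so a weight-adjusted model could be run later, but it would not be prespecified. That matters somewhat here: the study is open-label, and Protocol 10.3.7 schedules a data review once PK data through about Day 57 are available from at least 12 subjects per group.

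**Working it through.** **Inputs from the documents.** CV 49% in every arm, 16 evaluable subjects per arm, 90% interval, 90% assurance and a target half-length of 0.32 (Protocol 10.1, SAP section 7). A single three-arm model (SAP 9.3.2) leaves 48 − 3 = 45 residual df.

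**Log-scale SD.** σ² = ln(1 + 0.49²) = 0.2152, so σ = 0.4639. The standard error of a difference is 0.4639 × √(2/16) = 0.164.

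**The plan's own figure.** Assured half-length = t(0.95, df) × σ × √(2/16) × √(χ²(0.90, df)/df).
- Two arms only, df = 30: 1.697 × 0.164 × 1.158 = 0.3225, which matches the stated value of about 0.32. The probability of a half-length of at most 0.32 is 0.888.
- The SAP's three-arm model, df = 45: 1.679 × 0.164 × 1.130 = 0.3114. The probability is 0.941.

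**With log weight added.** Multiply σ by √(1 − R²), use df = 44, and inflate the variance by 1 + 1/43 for the expected chance imbalance in the covariate. At R² = 0 this gives 1.680 × 0.4639 × √(2/16 × 44/43) × 1.132 = 0.3155.

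**R² (assumed).** Neither document gives a weight-exposure slope or an SD of log weight. I use R² = (slope × SD)²/σ² with slopes of 0.5 to 1.0 and SDs of 0.15 to 0.20. The mid case, for example, is (0.75 × 0.175)²/0.2152 = 8.0%.

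| Slope, SD of log weight | R² | Assured half-length | Change from 0.3114 | Equivalent change in subjects |
|---|---|---|---|---|
| No relation | 0% | 0.316 | 1.3% wider | about 3% fewer |
| 0.5, 0.15 | 2.6% | 0.311 | none | 0% |
| 0.75, 0.175 | 8.0% | 0.303 | 2.8% narrower | 6% more |
| 1.0, 0.20 | 18.6% | 0.285 | 8.6% narrower | 20% more |

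The last column is (0.3114/adjusted half-length)² − 1, net of the covariate's cost. Break-even is R² = 1 − (0.3114/0.3155)² = 2.6%. At R² = 0 the probability of a half-length of at most 0.32 falls from 0.941 to 0.923.

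**Simulation.** With three arms of 16 and 200,000 trials per scenario, the 90th percentile of the adjusted half-length was 0.316, 0.312, 0.303 and 0.285 in the four scenarios, against 0.311 unadjusted throughout. Coverage of the 90% interval was 0.899 to 0.901 for both models, so only the width changes.

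**The case against.** The strongest reply is that nothing is broken. A formulation-only model is a legitimate choice for a randomized parallel comparison, the precision target is met, and neither document sets an equivalence margin that a narrower interval could help to satisfy. Around a ratio of 1, the mid case moves the 90% limits only from 0.732–1.365 to 0.739–1.353. This stands, and it is why the point is optional.

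The benefit also rests on inputs outside the documents. This stands too. The low case sits exactly at break-even, and with an SD of 0.12 and a slope of 0.5, R² is 1.7% and the interval is 0.5% wider.

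The statement that the worst case stays within 0.32 depends on the three-arm model. Protocol 10.3.2.2 can be read as a separate model for the primary comparison. With two arms, an uninformative covariate takes the half-length from 0.3225 to 0.329, the probability of meeting 0.32 from 0.888 to 0.852, and break-even to about 4.1%. The arithmetic is right, but SAP section 3 says the SAP supersedes the protocol's statistical considerations, and SAP 9.3.2 specifies a single model.

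Finally, the gain for Cmax is not quantified. At the stated Cmax CV of 23%, the high-case inputs would imply R² = 0.04/ln(1 + 0.23²) = 78%, so the AUC assumptions should not be carried over. This limits what can be said about Cmax but does not touch the primary AUC comparison. Later pooled population PK work (Protocol 10.3) could study weight, but it would not prespecify weight for this ratio.

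**Conclusion.** The point holds as a suggestion to consider, not as a defect. No baseline covariate is prespecified, and a plausible one is already collected. Under the SAP's three-arm model with 16 per arm and a CV of 49%, adding log weight changes the assured half-length by between 1.3% wider (weight explains nothing) and 8.6% narrower (R² of 18.6%), with a mid case of 2.8% narrower. The likely gain is modest and could be nil. It rests on the assumed slope and SD of log weight, and on log exposure being roughly linear in log weight with the same slope in each arm. The downside is small and stays inside the precision the plan promises.

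**What to change.** Consider prespecifying log screening body weight as a continuous covariate in the single model for log DN-AUC(0-∞), DN-AUC(0-tlast) and DN-Cmax, for example `model log_pk = formulation log_weight`, with the same contrasts. Report the formulation-only model as a sensitivity analysis. Fix the choice before any PK data are reviewed; the natural point is SAP sign-off, which section 3 requires before first dosing.

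The cost is one SAP sentence, one model term and 1 of 45 residual df, with no new data collection. Because the primary model would then differ from Protocol 10.3.2.2, SAP section 11, which now reports no changes, needs an entry. The sensitivity analysis adds a second set of ratios, for three parameters and three comparisons.
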